### **Duration of exposure to investigational drug, control drug and combination partner**

The study treatment has the following components:

- Investigational drug: ribociclib/placebo
- Combination partner
  - ET: Any of letrozole, anastrozole and exemestane and GnRH agonist

The duration of exposure to ribociclib/placebo, ET will be summarized.

Duration of exposure to ribociclib/placebo and ET (tamoxifen, letrozole, anastrozole, exemestane and GnRH agonist) during the treatment phase will be calculated as:

**Duration of exposure (days) during the treatment phase** = (last date of exposure during the treatment phase) – (first date of exposure on/after randomization) + 1.

The last date of exposure during the treatment phase is defined as follows for ribociclib/placebo and ET:

- For ribociclib/placebo: the last date of exposure is defined as the date of last administration of ribociclib/placebo; the first date of exposure is defined as the date of first administration of ribociclib/placebo
- For ET: the last date of exposure during the treatment phase is defined as the date of last administration of any ET on/before the last date of exposure of ribociclib/placebo; the first date of exposure is defined as the date of first administration of any ET on/after randomization.
- In rare cases in which patient does not have any ribociclib/placebo but have ET on/after randomization, the last date of exposure of ET during the treatment phase is defined as the date of first exposure of ET on/after randomization

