#### 2.1.1 General definitions

##### Investigational drug and study treatment

*Investigational drug*, will refer to the ribociclib/placebo only. Whereas, *study treatment* will refer to ribociclib + endocrine therapy (ET) and placebo + ET. In this study, ET may include tamoxifen, letrozole, anastrozole or exemestane. For premenopausal women, ET also include GnRH agonist to suppress ovarian function. ET alone after discontinuation of the ribociclib/placebo is not considered a “study treatment”.

The term investigational treatment may also be referred to as *study treatment* which is used throughout this document.

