### **Date of first administration of study treatment**

The date of first administration of study treatment will be derived as the first date on/after randomization when a nonzero dose of any component of study treatment was administered as per the (e)CRF. (Example: if randomization date is 03-Jan-2015, and 1st dose of ribociclib is administered on 05-Jan-2015, and 1st dose of ET is administered on 03-Jan-2015, then the date of first administration of study treatment is on 03-Jan-2015).

ET prior to and on/after randomization will be entered in the Adjuvant Endocrine Therapy eCRF page. First date on/after randomization of ET will be derived based on the start and end dates in the eCRF. (Example: randomization date is 03-Jan-2015, if ET with non-zero dose has a start date of 15-Dec-2014 and an end date on/after randomization, then first date on/after randomization of ET will be 03-Jan-2015; if ET start date is 15-Dec-2014 and end date is 02-Jan-2015, then restarts non-zero dose on 04-Jan-2015, then first date on/after randomization of ET will be 04-Jan-2015; in special cases in which start date is before randomization and end date is missing, then patient is ongoing and first date on/after randomization of ET will be date of randomization)

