### **2.3.1 Patient disposition**

Enrollment by country and center will be summarized for all screened patients and also by treatment arm using the FAS. The number (%) of randomized patients included in the FAS will be presented overall and by treatment group.. The number (%) of patients in the FAS who are still on treatment, who discontinued the study phases and the reason for discontinuation will be presented overall and by treatment group.

The following summaries will be provided (with % based on the total number of FAS patients):

- Number (%) of patients who were randomized (based on data from IRT system)
- Number (%) of patients who were randomized but not treated (based on eCRF page not completed for any study treatment component, 'DAR' eCRF page for ribociclib/placebo, 'Adjuvant endocrine therapy' eCRF page for ET and 'GnRH (Gonadotropin-Releasing Hormone) Agonist Therapies' eCRF page for GnRH; for ET and GnRH page, only dose administered on/after randomization will be considered)
- Primary reason for not being treated (based on "End of Treatment Phase Completion" eCRF page)

- Number (%) of patients who were treated (based on eCRF pages of each study treatment component completed with non-zero dose administered)
- Number (%) of patients who are still on-treatment (based on the ‘End of Treatment Phase’ page not completed);
- Number (%) of patients who discontinued the study treatment phase (based on the ‘End of Treatment Phase’ page)
- Primary reason for study treatment phase discontinuation (based on the ‘End of Treatment Phase’ page)

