## **2.4 Treatments (study treatment, rescue medication, concomitant therapies, compliance)**

### **2.4.1 Study treatment adherence/ compliance**

Duration of exposure, will be summarized by treatment arm, for ribociclib/placebo. Exposure summaries for ET and GnRH will also be summarized by treatment arm. Duration of exposure will be categorized into time intervals; frequency counts and percentages will be presented for the number (%) of subjects in each interval.

Subject level listings of all doses administered on treatment (for ET, also after the treatment phase) along with dose change reasons will be produced.

The safety set will be used for all summaries and listings of study treatment.

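### Does the changing wording for endocrine therapy (GnRH agonist in or out, tamoxifen missing from one list) leave day 1 and ET exposure undefined?

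*SAP*

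**What the plan says.** Section 2.1.1 (Investigational drug and study treatment) lists tamoxifen, letrozole, anastrozole and exemestane as ET and adds: "For premenopausal women, ET also include GnRH agonist to suppress ovarian function".

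Section 2.1.1 (Date of first administration of study treatment) sets day 1 at the first nonzero dose of any component on or after randomization, as recorded in the eCRF. On the ET date it says: "ET prior to and on/after randomization will be entered in the Adjuvant Endocrine Therapy eCRF page". An ET record that spans randomization, or that starts before it and has no end date, counts from the randomization date.

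Section 2.3.1 counts patients randomized but not treated. It names a separate page, "GnRH (Gonadotropin-Releasing Hormone) Agonist Therapies", and adds the condition "for ET and GnRH page, only dose administered on/after randomization will be considered".

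Section 2.4.1 opens with "Exposure summaries for ET and GnRH will also be summarized by treatment arm". Its component list then reads "ET: Any of letrozole, anastrozole and exemestane and GnRH agonist". The sentence that introduces the formula reads "Duration of exposure to ribociclib/placebo and ET (tamoxifen, letrozole, anastrozole, exemestane and GnRH agonist) during the treatment phase will be calculated as". For ET, "the first date of exposure is defined as the date of first administration of any ET on/after randomization".

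**The concern.** ET appears to mean different sets of drugs in different places. GnRH agonist is inside ET in 2.1.1 and in the 2.4.1 lists, but stands beside ET in 2.3.1 and in the opening of 2.4.1. Tamoxifen is in 2.1.1 and in the exposure sentence, but not in the component list.

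The GnRH point seems to have consequences. The only rule for the first ET date names a page that, by 2.3.1, does not hold GnRH records. That rule also counts a spanning record from randomization, whereas 2.3.1 speaks of doses given on or after randomization. Two programmers might therefore derive different start dates for the same patient.

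The start of study treatment fixes the safety study day, the safety baseline and the opening of the on-treatment period. The adverse event and laboratory tables that form the primary endpoint rest on these. The first ET date also sets the duration of ET exposure.

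**Working it through.** **1. The plan's own date examples.** With randomization on 03-Jan-2015, the 2.1.1 rules return the dates that the SAP states:
- ribociclib on 05-Jan and ET on 03-Jan give 03-Jan;
- an ET record from 15-Dec-2014 that runs past randomization, or has no end date, gives 03-Jan;
- an ET record that ends on 02-Jan and restarts on 04-Jan gives 04-Jan.

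**2. Which drugs count.**
- 2.1.1 puts GnRH agonist in ET, and the day-1 rule covers any component without limiting it to a page.
- 2.4.1 names GnRH agonist in both the component list and the exposure sentence.
- The document history (23-Feb-2020) records that GnRH was deliberately combined with ET for exposure reporting.
- Reading only the Adjuvant Endocrine Therapy page would let a sentence about data entry override these statements. For exposure it would contradict 2.4.1 outright.

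**3. Whether 2.3.1 conflicts with 2.1.1.** The condition in 2.3.1 is a parenthesis on counting patients randomized but not treated. It does not derive a date. It covers the ET and GnRH pages alike, so it sets no special rule for GnRH. It is compatible with 2.1.1, where an ongoing record is taken as administration from randomization.

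**4. What remains open.** Does a GnRH record that starts before randomization count from randomization (span rule) or from the next dose (dose-date rule)?

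The example uses the SAP's dates: randomized 03-Jan-2015, GnRH record from 15-Dec-2014 with no end date. Assumed: a 28-day injection interval, oral ET and ribociclib both starting on 15-Jan, oral ET ongoing, last ribociclib on 30-Jun-2015.
- Next injection: 15-Dec-2014 + 28 days = 12-Jan-2015.
- Day 1: 03-Jan (span) or 12-Jan (dose date), a gap of 9 days.
- ET exposure = last − first + 1. 30-Jun is day 181 of 2015, so it is 181 − 3 + 1 = 179 days, or 181 − 12 + 1 = 170 days.
- The page-only reading would give 15-Jan and 181 − 15 + 1 = 167 days, but step 2 rules it out.

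**5. Other assumed cases.** Randomization 03-Jan-2015, ribociclib from 10-Jan-2015 to 10-Jan-2016, injections every 28 days. GnRH starts on 15-Dec-2014 except in B. Oral ET runs from 10-Jan-2015 in A and B and from 20-Dec-2014 in C and D. It ends with ribociclib, except in D.

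| Case | Day 1: span / dose date | ET days: span / dose date |
|---|---|---|
| A: GnRH ongoing, oral ET not yet started | 03-Jan / 10-Jan | 373 / 366 |
| B: GnRH first given 05-Jan | 05-Jan / 05-Jan | 371 / 371 |
| C: oral ET and GnRH both ongoing | 03-Jan / 03-Jan | 373 / 373 |
| D: as C, oral ET stops 11-Nov-2015 (60 days before ribociclib) | 03-Jan / 03-Jan | 373 / 346 |

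Between these two rules, day 1 differs only where GnRH is ongoing at randomization, oral ET is not, and neither oral ET nor ribociclib/placebo starts on the randomization date. In D only the exposure duration differs, by 373 − 346 = 27 days, because GnRH is then the only ET still being given when ribociclib ends.

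**6. Tamoxifen.** The sentence that governs the calculation includes it, as does 2.1.1. Section 1.1 says patients who continued ribociclib were offered ET excluding tamoxifen, which may explain the shorter list. No derived value changes.

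**The case for a change.** The strongest case for a change is that agreeing which drugs count does not say how the GnRH date is derived. The one ET date rule names the wrong page for GnRH. For a drug given at intervals (an assumption, since the SAP gives no GnRH schedule), a record spanning randomization does not mean a dose was given that day. In the step 4 example, an adverse event on 08-Jan is treatment-emergent under the span rule and pre-treatment under the dose-date rule. Choosing between them after seeing the data would be undesirable, and the remedy is a few lines.

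Part of this stands. No sentence names the GnRH page in the date rule or says expressly that the span rule covers GnRH. But the natural reading gives one answer: GnRH is ET, and 2.1.1 derives the ET date from recorded start and end dates, so the span rule applies and day 1 is 03-Jan. Neither choice has been shown to give a wrong result. The example also needs a 12-day wait from randomization to both oral ET and ribociclib, and an event placed inside that wait. No test depends on the choice, and under 2.1.1 and 2.7.1 an event outside the window is still listed and flagged.

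**Conclusion.** No change to the plan follows. The set of drugs is settled by 2.1.1 and the exposure sentence in 2.4.1, and the missing tamoxifen is a clerical slip. The claimed clash between 2.1.1 and 2.3.1 does not hold up.

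The remaining gap is how to date a GnRH record that begins before randomization. Analysts would fill it sensibly by applying the ET rule already written. Between the two tenable rules, the assumed cases move day 1 by 0 to 9 days and ET exposure by 0 to 27 days. Day 1 does not move at all when oral ET is already running at randomization. These sizes rest on assumed start dates, stop dates and injection interval. The number of GnRH patients is not given, so the effect on the tables cannot be computed from the SAP. In a descriptive safety study with full flagged listings, this is a matter for the derivation specification.

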#### **2.4.2 Primary endpoint**

The primary endpoints of this study are the tolerability and safety of the treatment regimen based on frequency and severity of AEs, laboratory and ECG abnormalities. Descriptive summaries of key safety and baseline characteristics will be provided. These include summaries of treatment duration exposure, adverse events, labs, and ECG findings. The details can be found in [section 2.7](#).

#### **2.4.3 Handling of missing values/censoring/discontinuations**

Not applicable

#### **2.4.4 Supportive analyses**

Not applicable

#### **2.5 Analysis of the key secondary objective**

Not applicable

#### **2.6 Analysis of secondary efficacy objective(s)**

Not applicable

#### **2.7 Safety analyses**

All safety analyses will be based on the safety set.

##### **2.7.1 Adverse events (AEs)**

AE summaries will include all AEs occurring during on treatment period. All AEs collected in the AE (e)CRF page will be listed along with the information collected on those AEs e.g. AE

relationship to study drug, AE outcome etc. AEs with start date outside of on-treatment period will be flagged in the listings.

AEs will be summarized by number and percentage of subjects having at least one AE, having at least one AE in each primary system organ class (SOC) and for each preferred term (PT) using MedDRA coding. A subject with multiple occurrences of an AE will be counted only once in the respective AE category. A subject with multiple CTCAE grades for the same preferred term will be summarized under the maximum CTCAE grade recorded for the event. AE with missing CTCAE grade will be included in the 'All grades' column of the summary tables.

In AE summaries, the primary system organ class will be presented alphabetically and the preferred terms will be sorted within primary SOC in descending frequency. The sort order for the preferred term will be based on their frequency in the ribociclib + ET arm.

The following adverse event summaries will be produced by treatment arm; overview of adverse events and deaths (number and % of subjects who died, with any AE, any SAE), AEs by SOC and PT, summarized by relationship (all AEs and AEs related to study treatment), seriousness (SAEs and non-SAEs), leading to treatment discontinuation, and leading to fatal outcome. In addition, a summary of serious adverse events with number of occurrences will also be produced (an occurrence is defined as >1 day between start and prior end date of record of same preferred term).

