### 1.1 Study design

This was a randomized, phase III, double-blind, placebo-controlled, multi-center, international study to evaluate efficacy and safety of ribociclib with ET as an adjuvant treatment in patients with HR-positive, HER2-negative, high risk early breast cancer.

Following the protocol amendment 02, this study is now an open label, multi-center phase II conducted in the U.S only. The study has been closed to enrollment. All randomized patients were unblinded; patients randomized to placebo permanently discontinued study treatment and patients randomized to ribociclib were offered the option to continue treatment with ribociclib + ET (excluding tamoxifen). Patients randomized to placebo have to complete 30-day safety follow up after the last dose of placebo.

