**Table 1-1 Objectives and related endpoint**

Objective	Endpoint
Primary To evaluate the preliminary safety and tolerability of the ribociclib + ET in patients that were randomized to ribociclib + ET prior to the early closure of enrollment.	Tolerability and Safety of the treatment regimen based on frequency and severity of AEs, laboratory and ECG abnormalities

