#### Data included in the analysis

All data collected up to the last patient last visit will be used in the analysis.

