#### General analysis conventions

**Pooling of centers:** Unless specified otherwise, data from all study centers will be pooled for the analysis. Due to expected small number of patients enrolled at centers, no center effect will be assessed. Protocol deviations, number of patients in analysis populations and discontinuations from study treatment will be summarized by center.

**Qualitative data** (e.g., gender, race, etc.) will be summarized by means of contingency tables by treatment group; a missing category will be included as applicable. Percentages will be calculated using the number of patients in the relevant population or subgroup as the denominator.

**Quantitative data** (e.g., age, body weight, etc.) will be summarized by appropriate descriptive statistics (i.e. mean, standard deviation, median, minimum, and maximum) by treatment group.

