### **Date of last administration of study treatment**

The date of last administration of study treatment is defined as the last date when a non-zero dose of study treatment was administered as per (e)CRF. For patients who take at least one dose of ribociclib/placebo, date of last administration of study treatment is the last date when a non-zero dose of ribociclib/placebo was administered. So date of last administration of study treatment is the same as date of the last administration of investigational drug for these patients. For patients who only take ET on/after randomization but no ribociclib/placebo, date of last administration of study treatment is defined as the date of first administration of study treatment.

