### **On-treatment assessment/event and observation periods**

For adverse event reporting the overall observation period will be divided into three mutually exclusive segments, based on AE start date:

1. ***pre-treatment period***: from day of patient’s informed consent to the day before first administration of study treatment
2. ***on-treatment period***: from date of first administration of study treatment to 30 days after date of last actual administration of any study treatment (including start and stop date)
3. ***post-treatment period***: starting at day 30+1 after last administration of study treatment.

Safety summaries (tables, figures) include only data from the on-treatment period with the exception of baseline data which will also be summarized where appropriate (e.g. change from baseline summaries). In addition, a separate summary for death including on treatment and post treatment deaths will be provided. In particular, summary tables for adverse events (AEs) will summarize only on-treatment events, with a start date during the on-treatment period (***treatment-emergent*** AEs).

However, all safety data (including those from the post-treatment period) will be listed and those collected during the pre-treatment and post-treatment period will be flagged.

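### Side-by-side on-treatment percentages will cover different windows by arm to the extent that ribociclib patients continued after unblinding, and section 2.7 plans neither a common cut nor a caveat

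*SAP*

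**What the plan says.** Section 1.1 of the SAP states that after unblinding "patients randomized to placebo permanently discontinued study treatment and patients randomized to ribociclib were offered the option to continue treatment". Placebo patients then complete a 30-day safety follow-up. On the data to be used, section 2.1 says: "All data collected up to the last patient last visit will be used in the analysis".

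The window for safety summaries (section 2.1.1) runs "from date of first administration of study treatment to 30 days after date of last actual administration of any study treatment". For anyone who took ribociclib or placebo, the "date of last administration of study treatment is the last date when a non-zero dose of ribociclib/placebo was administered". Endocrine therapy does not lengthen it: "ET alone after discontinuation of the ribociclib/placebo is not considered a" study treatment.

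Within that window, section 2.7.1 plans that "AEs will be summarized by number and percentage of subjects having at least one AE", and the list of AE summaries is by treatment arm. Sections 2.7.2 (on-treatment deaths), 2.7.4.1 (notable ECG values) and 2.7.4.2 (notable vital signs and change to the worst value) also name the arm. The AESI, laboratory and liver paragraphs do not. For these, by-arm presentation follows only from the general convention that qualitative data "will be summarized by means of contingency tables by treatment group", with numbers of patients as denominator.

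Table 1-1 gives one objective: "To evaluate the preliminary safety and tolerability of the ribociclib + ET in patients that were randomized to ribociclib + ET" before enrollment closed early. Section 2.4.2 makes the endpoint descriptive, and section 2.4.1 summarizes duration of exposure by arm.

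**The concern.** The length of the on-treatment window follows each patient's own time on ribociclib or placebo. After unblinding that time could grow in one arm only. A crude percentage of patients with at least one event rises with the length of observation whenever the risk persists. The ribociclib percentage can then exceed the placebo percentage with no drug effect.

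Two of the AE summaries in section 2.7.1 show the asymmetry plainly. AEs leading to treatment discontinuation cannot accrue on placebo once placebo has been stopped for everyone, but can still accrue in ribociclib patients who continue. AEs judged related to study treatment mix attributions made before and after the treatment was known; the later ones can run long for ribociclib and only through the 30-day tail for placebo.

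At stake is the use of the placebo column as a reference. Section 2.7 has no cut at unblinding and no caveat. The only table footnotes that the SAP specifies are the versions of the case retrieval strategy and of MedDRA.

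**Working it through.** The SAP states no figure to reproduce: no sample size, unblinding date, exposure, uptake of continuation or event rate. What follows illustrates the mechanism; **every duration, hazard and share is an assumption**.

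**How long the gap could be.** The document history puts the protocol amendment in April 2018 and the latest SAP update, still before database lock, on 23 February 2020. That is 664 to 693 days, or 21.8 to 22.8 months at 30.4375 days per month. This gives a rough scale only, because the SAP gives neither the unblinding date nor actual durations.

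**Model.** The constant monthly hazard λ is the same in both arms. With T months on drug and a 1-month tail for the 30 days:

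- I(T) = 1 − exp(−λ(T + 1))
- Placebo = I(Tp)
- Ribociclib = c·I(Tr) + (1 − c)·I(Tp), where c is the share who continue

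Worked case, λ = 0.02, Tp = 5, Tr = 18:

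- Placebo: 1 − exp(−0.12) = 11.3%
- Continuers: 1 − exp(−0.38) = 31.6%
- c = 0.3: 0.3 × 31.6% + 0.7 × 11.3% = 17.4%, a ratio of 1.54

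| λ per month | Tp / Tr (months) | Placebo | Ribociclib, c = 0.3 | c = 0.5 | c = 1 |
|---|---|---|---|---|---|
| 0.02 | 5 / 18 | 11.3% | 17.4% (1.54) | 21.5% (1.90) | 31.6% (2.80) |
| 0.05 | 5 / 18 | 25.9% | 36.5% (1.41) | 43.6% (1.68) | 61.3% (2.37) |
| 0.10 | 8 / 12 | 59.3% | 63.4% (1.07) | 66.0% (1.11) | 72.7% (1.23) |

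Ratios to placebo are in brackets.

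**Cases with little or no distortion, or the reverse.**

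- Nobody continues and nobody stops early: ratio 1.0.
- All risk in the first 2 months (0.10 per month): 1 − exp(−0.2) = 18.1% in both arms, ratio 1.0.
- 0.10 per month for 2 months, then 0.01, with 5 / 18 months: 21.3% on placebo against 24.2%, 26.1% and 30.9% for c = 0.3, 0.5 and 1 (1.14, 1.23, 1.45).
- 20% of ribociclib patients stop at 2 months, λ = 0.02, 5 / 18 months: ribociclib is 0.2·I(2) + c·I(18) + (0.8 − c)·I(5). This gives 16.3% for c = 0.3 (1.44), 11.2% for c = 0.05 (0.99) and 10.2% for c = 0 (0.90).

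**Worst-value summaries.** With one visit a month and independent visit errors, the expected maximum of 6 values is 1.27 within-patient SD and of 19 values 1.84 SD, with no true change. If few assessments were made after unblinding, the difference is smaller.

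**Effect of a cut at unblinding** (λ = 0.02, month 5, no tail). Without early stopping, both arms show 1 − exp(−0.10) = 9.5%. If 20% of ribociclib patients stop at 2 months, their window ends at month 3. Ribociclib then shows 0.2 × (1 − exp(−0.06)) + 0.8 × 9.5% = 8.8%, a ratio of about 0.92. The cut removes the effect of continuation but not that of earlier discontinuation.

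**Exposure-adjusted rates are no safe substitute.** With the early-only hazard above and 5 / 18 months, first events per 100 patient-years are 42.8 on placebo against 20.9 (c = 0.5) or 13.8 (c = 1) on ribociclib, with no true difference.

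**The case against.** The strongest reply is that no planned analysis is wrong. The only objective concerns the ribociclib + ET patients, the endpoint is descriptive, and no between-arm test is planned. This stands, and it limits the point to how the tables are presented.

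The imbalance is also disclosed. Section 1.1 describes the placebo stop and the offer to continue. Section 2.3.1 tabulates discontinuation with its primary reason by group, section 2.4.1 tabulates exposure by arm and in intervals, and study day appears in the listings. A careful reader is therefore not left unaware. But none of this changes the percentages, and none of it is linked to the tables it qualifies.

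A reader might infer that the safety results are biased against ribociclib. The SAP does not support this. Continuation was only offered, uptake and duration are not given, and the illustrations include ratios of 1.0 and below. Nor can the windows be called unequal for every patient: they diverge by design only for those who continued. ECG summary statistics by time point are less exposed, since they are presented visit by visit.

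Finally, repeating every safety table at a cut would be out of proportion for a descriptive study with no between-arm objective. That also stands, and the change proposed is limited accordingly.

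**Conclusion.** The point holds as a cheap improvement. The on-treatment rule, applied after one arm was stopped and the other was offered continuation, gives by-arm percentages over systematically different windows to the extent that the offer was taken up. This applies directly to AEs, on-treatment deaths, notable ECG values and notable vital signs. It applies to AESIs and to laboratory and liver tables only through the general by-group convention.

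The ribociclib + ET column remains valid for its objective. Only a comparison across columns can mislead, and neither its size nor its direction can be derived from the SAP. The range of 0.90 to 2.80 rests wholly on the assumed hazards, durations, continuation shares and early stopping. Confidence is high in the reading of the window rules, not in any particular amount of distortion.

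**What to change.** In section 2.7:

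1. Keep the full on-treatment tables as the main output.
2. Footnote every full-period by-arm percentage table to say that the windows differ by arm after unblinding, with a reference to the exposure table of section 2.4.1.
3. Add a limited set of supplementary by-arm tables: AE overview, AEs by system organ class and preferred term, AESIs, and notable laboratory, liver and ECG values. Count events up to the earlier of the unblinding date and the end of the on-treatment period. Show later events separately for both arms, including the 30-day tails of placebo patients and of ribociclib patients who declined to continue.
4. State that these tables remove the continuation imbalance created by unblinding but not differences from earlier discontinuation, and that any between-arm description should use them.

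The cost is some SAP wording, one footnote and a few tables with fewer events (in the illustration 9.5% instead of 11.3% on placebo at 0.02 per month, the remainder being shown separately). An unblinding date is needed for each patient, or one date for the study, and the SAP does not say that either is captured. If the extra tables are declined, the footnote alone costs almost nothing and should still be added.
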